3.3 Visit 2 (Treatment Periods 1, 2, and 3)

3.3.1 Period 1

Subjects will report to the CRU on the morning of Day 1.

3.3.1.1 Day 1

- Review of medical history;
- Review of medications and supplements;
- Measurement of vital signs (weight, seated SBP/DPB, and heart rate);

- Provide the first dose of single-blind placebo at least 45 minutes prior to breakfast;
- Provide breakfast;
- Subjects will be fitted with the continuous glucose monitoring (CGM) device and data recording will begin;
- Provide 4 doses (8 capsules) of single-blind placebo and instruct subjects to take one dose at least 45 minutes before lunch, one dose at bedtime, one dose at least 45 minutes before breakfast on Day 2, and one dose at least 45 minutes before lunch on Day 2.
- Adverse events will be monitored and recorded.
- Subjects will be instructed to return to the CRU at approximately 5pm (± 30 minutes) on Day 2.

3.3.1.2 Day 2

- Admission to the CRU at approximately 5pm (± 30 minutes);
- Review of medications and supplements;
- Measurement of vital signs (weight, seated SBP/DPB, heart rate, and temperature);
- Perform breathalyzer;
- Collect a urine sample for:
 - Drug screen;
 - Pregnancy testing (WCBP only)
- Provide a standardized diabetic meal at approximately 7pm (± 60 minutes). Standardized meals will continue throughout the remainder of the study Period.
- Provide a dose of single-blind placebo at approximately 10pm (± 60 minutes).
- Continue CGM monitoring;
- Adverse events will be monitored and recorded.

3.3.1.3 Day 3

- Review of medications and supplements;
- Measurement of vital signs (weight, seated SBP/DPB, heart and rate);
- Provide a dose of single-blind placebo at approximately 7am (± 60 minutes);
- Provide breakfast no sooner than 45 minutes after the morning dose;
- Provide a dose of single-blind placebo at approximately 1pm (± 60 minutes), at least 45 minutes prior to lunch;
- Provide lunch no sooner than 45 minutes after the afternoon dose;

- Provide dinner at approximately 7pm (\pm 60 minutes);
- Provide a dose of single-blind placebo at approximately 10pm (\pm 60 minutes);
- Collect a blood sample according to schedule (per randomization scheme, either morning, afternoon, or evening) prior to the specified dose of placebo for:
 - Pre-dose PD analysis
 - Serum chemistry
- Collect scheduled (per randomization scheme) postdose PD blood draws every 30 minutes (\pm 5 minutes) until 5 hours has elapsed;

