5.2 Randomization

This is a single center, randomized, double-blind, 3-way crossover study. Approximately 30 eligible subjects will be randomized to placebo and 2 of the 3 possible dose groups: ORMD-0801 460 IU qd (in the evening), ORMD-0801 460 IU bid (in the morning and evening) and ORMD-0801 460 IU tid (morning, afternoon, and evening).

In order to estimate the morning, afternoon, and evening PD effect, each subject will have one period in which the PD blood samples are drawn in the morning, one period in which the PD blood samples are drawn in the afternoon and one period in which the PD blood samples are drawn in the evening. When the subject is on active therapy, the PD blood samples will be drawn after an active therapy dose (not after the placebo dummy). Thus, if the subject is taking ORMD-0801 460 IU qd, the PD blood samples will be drawn in the evening. If the subject is taking ORMD-0801 460 IU bid, the PD blood samples will be drawn in the morning or evening. If the subject is taking ORMD-0801 460 IU tid or placebo, the PD blood samples will be drawn in the morning, afternoon, or evening.

Integrium, LLC will generate and implement the randomization procedures for this trial. A computer-generated randomization schedule will be used for assigning treatment (active or placebo). The Investigational Site pharmacist will follow this randomization schedule to dispense the appropriate study treatment.

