5.8 Dietary Restrictions

Subjects will fast overnight for at least 8 hours prior to the clinical safety labs at Screening.

Subjects should not take any food for at least 45 minutes or more prior to scheduled ORMD-0801 (or placebo) dosing as described in the study design. All subjects will be provided with a standardized diabetic breakfast on Day 1, then continuing from dinner on Day 2 through breakfast on Day 10. Standardized snacks will be provided between breakfast and lunch, between lunch and dinner, and between dinner and bedtime.

Excessive caffeine use (i.e., more than five cups of caffeinated beverages per day) will not be allowed from Screening through the Follow-Up Visit 3. Excessive alcohol use or binge drinking will be discouraged during the study, and alcohol will be prohibited 72 hours prior to admission to the CRU (Visit 2/Period 1, 2, and 3/Day 1) and throughout the domiciled period (i.e., through the morning assessments on Day 10).

Subjects will also be asked to refrain from any unusual or unaccustomed vigorous exercise during the course of the study.

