2.8.2. Pharmacokinetic / Pharmacodynamic Evaluations

Since Insulin is present in the subjects regardless of treatment, standard PK derivations do not apply.

The PK/PD measurements are taken pre-treatment (Day 3) and at end of treatment (Day 8). On Day 3, all subjects received Placebo, so these measurements will be used as the within subject control.

Time matched changes between Day 8 and Day 3 will be derived for the PK and PD parameters for each subject.

The following time intervals will be summarized: 0 to 60 minutes, 60 to 120 minutes, 120 to 180 minutes, 180 to 240 minutes, 240 to 300 minutes, 120 to 300 minutes and 180 to 300 minutes. Please note that the 0 to 60 minute interval will not be summarized, since it is believed that the study drug takes 60 minutes to metabolize.

The following parameters will be derived for Insulin C-Peptide for each subject:

- Positive Area (Area above 0),
- Negative Area (Area below 0),
- Absolute Area (Positive Area + the absolute value of the Negative Area),
- Maximum Difference,
- Time of Maximum Difference,
- Positive Area / hr (for the 120 to 300 minutes and 180 to 300 minutes intervals only),
- Negative Area / hr (for the 120 to 300 minutes and 180 to 300 minutes intervals only), and
- Absolute Area / hr (for the 120 to 300 minutes and 180 to 300 minutes intervals only).

The Positive Areas, Negative Areas and Absolute Areas will be compared using a one-way analysis of variance (ANOVA) with Fisher's LSD being used for pairwise treatment group comparisons.

The maximum difference and time of maximum difference will be compared in a pairwise fashion using the Wilcoxon Rank Sum test.

The PK/PD analysis will be conducted using model-independent methods and will be based on plasma concentrations of insulin and C-peptide. Individual plasma concentrations of insulin and C-peptide will be listed for each subject and sampling time and summarized descriptively using the arithmetic mean, SD, CV (%), median, minimum and maximum. Individual plasma concentration-time profiles of insulin and C-peptide will be plotted on both a linear and a semi-logarithmic scale. Mean values will also be presented graphically.

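### SAP 2.8.2 tests the insulin and C-peptide results as independent records with no subject, period or sampling-slot term, although Protocol 5.2 samples qd only in the evening and the placebo period of a qd subject only in the morning or afternoon

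*SAP*

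**What the plan says.** **SAP 2.8.2.** The analysed quantity is a within-period change: "Time matched changes between Day 8 and Day 3 will be derived for the PK and PD parameters for each subject". Day 3, when everyone takes placebo, serves as the within-subject control. For the areas, "The Positive Areas, Negative Areas and Absolute Areas will be compared using a one-way analysis of variance (ANOVA"), followed by Fisher's LSD for pairs of regimens. The largest difference and its timing "will be compared in a pairwise fashion using the Wilcoxon Rank Sum test". No subject, period or sampling-time term is named, and the text contains no summary by sampling time.

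**Protocol 5.2.** Each subject gets placebo and two of the three active regimens. The purpose of the sampling scheme is stated: "In order to estimate the morning, afternoon, and evening PD effect". The slots are therefore rotated over the three periods: "each subject will have one period in which the PD blood samples are drawn in the morning", and the afternoon and evening are likewise used once each. Active periods are sampled after an active dose. Hence "if the subject is taking ORMD-0801 460 IU qd, the PD blood samples will be drawn in the evening"; bid is sampled in the morning or evening, and tid and placebo in any slot.

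**Context.** Comparing insulin and C-peptide with placebo is a secondary objective (SAP 1.3.2), and SAP 2.11 says the study is not powered. Protocol 8.2 describes only descriptive PK/PD summaries. The randomization plan (SAP 2.12) and the table shells (SAP 4.3) are separate files.

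**The concern.** There are two faults.

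1. The planned tests assume independent records. Three records come from each subject, so the error term is wrong for a crossover even if time of day plays no part.
2. For qd, regimen and time of day are tied together. A qd subject's single evening slot is used in the qd period, so the qd-placebo contrast between periods is also evening against morning or afternoon.

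Subtracting Day 3 removes any constant level belonging to a subject, period or clock time. Two things survive. One is a Day 3 to Day 8 drift that differs by slot. The other is noise that differs by slot: the Positive, Negative and Absolute Areas are non-linear and grow with noise even when the mean change is zero, so unequal noise looks like a regimen difference.

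Either is plausible. On meals the protocol says "Standardized meals will continue throughout the remainder of the study Period", starting with dinner on Day 2, so Day 3 is the first full day on them and Day 8 the sixth. Breakfast or lunch may fall inside the morning or afternoon sampling window, while no meal is scheduled after the 10pm dose.

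At stake is whether a qd result, significant or null, can be compared with bid and tid as a dose response.

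**Working it through.** The plan gives no figure to reproduce here: SAP 2.11 states 30 subjects without an SD or effect size. Assumed throughout: 10 subjects per active pair, permitted slot patterns used about equally, SD of the change set to 1, nominal 5%. LSD is run without a prior F test unless stated; the SAP does not say which applies.

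**Step 1, permitted patterns** (M, A, E = morning, afternoon, evening).
- qd+bid: one pattern (qd E, bid M, placebo A).
- qd+tid: two (qd E; tid M with placebo A, or tid A with placebo M).
- bid+tid: four, one of which has placebo in E.

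Expected evening records: qd 20 of 20, bid 5 of 20, tid 2.5 of 20, placebo 2.5 of 30. No qd subject's randomized placebo period is in the evening.

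**Step 2, no slot effect.** LSD takes the SE of qd minus placebo as √(1/20 + 1/30) = 0.289. All 20 qd subjects also supply a placebo record, so the true value is √(1/20 + 1/30 − 2ρ/30): 0.252 at ρ = 0.3 and 0.224 at ρ = 0.5. With 90 − 4 = 86 df the critical t is 1.988. The effective cut-off is 1.988 × 0.289/0.252 = 2.28 at 0.3 and 2.57 at 0.5, which a normal approximation turns into 2.3% and 1.0%. Simulation gives about 2.5% and 1.2%.

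**Step 3, evening shift δ in the change, no drug effect.** The qd-placebo bias is δ × (1 − 2.5/30): 0.229 for δ = 0.25 and 0.458 for δ = 0.5. Divided by 0.252 these are 0.91 and 1.82. Against a cut-off of 2.28 the false-positive rates are 8.6% and 32%.

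| qd vs placebo, simulated | δ = 0.25 | δ = 0.5 |
|---|---|---|
| LSD, ρ = 0 | 12% | 33–34% |
| LSD, ρ = 0.3 | about 9% | 30–32% |
| LSD, ρ = 0.5 | 7% | 29–30% |
| LSD only after a significant F test, ρ = 0.3 | 3.5% | 17% |
| Rank-sum, ρ = 0.3 | 8.5% | 30% |

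The extreme allocations (placebo evening records 0 or 10 of 30) give 6–10% and 17–38% for LSD at ρ = 0.3. Bid and tid versus placebo stay at 2.3–3%.

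These figures use one normal score. The same shifts applied to simulated areas give about 11%, 7% and 4.5% (Positive, Negative, Absolute) at δ = 0.25, and 45%, 26% and 11% at δ = 0.5.

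**Step 4, unequal noise, no drug effect and no shift.** Areas over 120–300 minutes, subject share of variance 0.3, evening noise multiplied by k; LSD, qd vs placebo:

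| k | Positive Area | Absolute Area |
|---|---|---|
| 0.75 | 4% | 30% |
| 1 | 2% | 3% |
| 1.25 | 6.5% | 25% |
| 1.5 | 18% | 63% |

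Repeat simulations gave 28.5–34% at k = 0.75 and 61.5–68% at k = 1.5 for Absolute Area. At k = 0.75, requiring a significant F test first brings Absolute Area to about 14%.

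**Step 5, candidate remedies at ρ = 0.3, δ = 0.25 and 0.5.**
- Subject and period model without slot: 16% and 47%.
- Signed-rank test: 14% and 41%.
- Model with slot: 5.2% and 5.2%.
- Slot model applied to ranks: 5.3% and 4.9%.

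Under the unequal noise of Step 4, the slot model with a common variance gives about 2–10%. Pairing within subject without a slot term therefore sharpens the confounded contrast.

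**The case against.** The strongest reply is that the control already exists. Every qd period has its own evening Day 3 placebo profile, and the analysed change is taken against it. A reader might infer from the sampling rule that qd has no evening placebo at all. The documents do not support that: only the randomized placebo period lacks an evening sample. The effect of qd against its own evening Day 3 placebo is a legitimate quantity.

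A reader might also infer that the qd results will be biased. That is not shown. The documents give no slot-specific drift or noise, and with neither present the tests err on the cautious side. The bedtime snack ("Standardized snacks will be provided between breakfast and lunch, between lunch and dinner, and between dinner and bedtime") softens the meal contrast. If evenings are quieter, k below 1 is the relevant case and the largest figures, at k = 1.5, are not.

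It is equally tempting to make a slot-adjusted model the only basis for qd. That trades one untestable assumption for another. Take a response of 0.5 SD per dose with an evening multiplier of 0.5 or 1.5. Unadjusted qd minus placebo is then 0.25 or 0.75, which is the true evening effect; slot adjustment moves it to 0.41 or 0.59. The qd data cannot tell this case from a drift, so both models should be shown.

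Finally, a split by slot may exist in the separate table shells, so its absence can be asserted only for the SAP text. None of this answers the independence assumption or the qd confounding with time of day in SAP 2.8.2.

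**Conclusion.** The point holds in two parts.

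The independence assumption is wrong as written. Under positive within-subject correlation and no slot effect it makes the qd-placebo LSD test too conservative: about 2.5% at a correlation of 0.3 and 1.2% at 0.5.

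The tie between qd and evening sampling follows from Protocol 5.2. Separate randomization details cannot put a qd subject's placebo period in the evening without breaking that section. Its consequence is conditional: with an assumed evening drift or noise difference, false positives for qd versus placebo can exceed 5% several-fold, as Steps 3 and 4 show. The rates depend on the assumed size, the area chosen and whether an F test precedes LSD, and some combinations stay below 5%.

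Contrasts of bid and tid with placebo are little affected by an evening shift. The primary CGM endpoint is not involved, and the p-values are exploratory. The change should still be made, because the qd results will otherwise invite a dose-response reading that the sampling scheme cannot support.

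**What to change.** In SAP 2.8.2:

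1. Replace the one-way ANOVA/LSD on the areas with a crossover model containing subject, period, sampling slot and regimen. Show the same model without slot beside it, labelled as confounded with time of day for qd. An evening-specific residual variance may be a sensitivity analysis only, since 20 of the 30 evening records would be qd.
2. For the largest difference and its time, apply the same model to ranks or present results by regimen within slot. Do not use unadjusted rank-sum or signed-rank tests for qd contrasts.
3. Summarise all PK/PD parameters by regimen within morning, afternoon and evening.
4. State that slot adjustment assumes no slot-by-regimen interaction, that qd conclusions apply to the evening dose against its own evening Day 3 placebo, and that differences between qd and bid or tid are not read as dose response.
5. Check the randomization plan for estimability. With subject fixed, 3 of 45 combinations of pattern use leave the slot-adjusted qd contrast non-estimable, all with placebo sampled only in the afternoon. If that applies, report qd descriptively.

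**Cost.** SAP wording and programming only; no extra blood draws and no change to allocation. With equal pattern use, the variance of qd versus placebo rises about 2.4- to 3.0-fold in the slot-adjusted model; at a correlation of 0.3 the SE goes from 0.25 to 0.41 SD. The evening effect is separated from qd only through the bid+tid subjects (10 of 30 as assumed), and the by-slot summaries rest on few records.

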2.2 Secondary Objectives

- To compare pre-treatment (Day 3) to end of treatment (Day 8) mean daytime CGM glucose for single and multiple doses of ORMD-0801 vs placebo.
- To compare pre-treatment (Day 3) to end of treatment (Day 8) mean nighttime CGM glucose for single and multiple doses of ORMD-0801 vs placebo.
- To compare pre-treatment (Day 3) to post-treatment washout (Day 9) 24-hour CGM glucose for single and multiple doses of ORMD-0801 vs placebo.
- To compare post-prandial glucose measurements for single and multiple doses of ORMD-0801 vs placebo.
- To compare pre-treatment (Day 3) to end of treatment (Day 8) insulin pharmacokinetics (PK) for single and multiple doses of ORMD-0801 vs placebo.
- To compare pre-treatment (Day 3) to end of treatment (Day 8) C-peptide pharmacodynamics (PD) for single and multiple doses of ORMD-0801 vs placebo.
- To compare defined events of hypoglycemia for single and multiple doses of ORMD-0801 vs placebo.

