- ⁶A standardized breakfast will be provided on Day 1. Beginning with dinner on Day 2 and ending with breakfast on Day 10, breakfast and lunch will be provided no sooner than 45 minutes after corresponding treatment doses. Dinner will be provided at approximately 7pm (±60 minutes). Standardized snacks will be provided between breakfast and lunch, between lunch and dinner, and between dinner and bedtime.
- ⁷Blood samples (scheduled per randomization scheme) for insulin and C-peptide will be drawn pre-dose and every 30 minutes (± 5 minutes) postdose until 5 hours has elapsed.
- ⁸Randomization will occur on the morning of Period 1/Day 4. Crossover will occur on the morning of Period 2/Day 4 and then again on the morning of Period 3/Day 4.
- ⁹Subjects will receive their assigned randomized treatment from the morning of Day 4 through the evening of Day 8. Doses will be administered at approximately 7am (±60 minutes), 1pm (±60 minutes), and 10pm (±60 minutes).

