5 STUDY TREATMENT

5.1 Description of Investigational Drug

Active:

Code name: ORMD-0801

Dosage form: 2 soft gel capsules per dose

Strength: 230 IU insulin (8 mg insulin) per capsule

Description: API (recombinant human insulin USP), in Oramed's proprietary formulation [aprotinin, SBTI, disodium EDTA, fish oil, and TWEEN 80] in capsules.

Placebo control:

Fish oil in capsules, identical in appearance to ORMD-0801

Note: 230 IU Insulin and placebo capsules are all identical in appearance.

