5.3 Study Treatment Administration

5.3.1 Study Treatment Periods

In order to achieve the desired 460 IU, 2 capsules will be administered per dose. Accordingly, subjects who are randomized to placebo will also receive 2 identical placebo capsules per dose.

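### Each 5-hour PK/PD window nominally follows one 460 IU dose in qd, bid and tid alike, so the active-versus-active comparisons in SAP 2.8.2 do not directly measure single versus multiple daily dosing

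*SAP*

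**What the plan says.** Protocol 2.2 lists as a secondary objective the comparison of "insulin pharmacokinetics (PK) for single and multiple doses of ORMD-0801 vs placebo", with a matching objective for C-peptide. Protocol 5.3.1 fixes the dose: "In order to achieve the desired 460 IU, 2 capsules will be administered per dose". Samples are drawn predose and "every 30 minutes (± 5 minutes) postdose until 5 hours has elapsed" (Protocol 3.6, footnote 7; also 6.5), on Day 3 and Day 8 of each period.

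Protocol 5.2 gives the reason for the scheme: "In order to estimate the morning, afternoon, and evening PD effect, each subject will have one period" sampled in each of the three parts of the day. It adds that, on active therapy, the sampled dose must be an active one and not the dummy.

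SAP 2.8.2 takes the Day 8 minus Day 3 difference at matched times. It compares the areas by one-way ANOVA, "with Fisher's LSD being used for pairwise treatment group comparisons", and compares the maximum difference and its time pairwise by the Wilcoxon rank sum test. It has no term for sampling slot and no estimate by slot. The insulin and C-peptide tables in SAP 4.1 are titled by time point and by time interval only, and SAP 2.10 plans no other analyses.

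**The concern.** What separates bid and tid from qd is the additional daily doses. The samples follow only one dose, of the same size in each regimen, so a comparison of tid with qd on these areas does not sample what the extra doses contribute. If the regimen means are similar, a reader of the tables could conclude that further daily doses add no exposure. If they differ, the difference could come from carry-over or from the hour of sampling. Meanwhile the question the scheme was built for, namely what one dose does in the morning, afternoon and evening, receives no analysis.

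**Working it through.** **Inputs.** Capsule strength is "230 IU insulin (8 mg insulin) per capsule" (Protocol 5.1), with 2 capsules per dose. Dosing is at about 7am, 1pm and 10pm, each ±60 minutes (Protocol 3.6, footnote 9). Active slots are evening for qd, morning and evening for bid, and all three for tid (Protocol 5.2). One draw is 4.5 mL (Protocol 6.5). For Day 8 I follow Protocol 5.2 and 6.5. The Day 8 procedures in Protocol 3.3 tie the sample to a placebo dose, which conflicts with those sections and must be reconciled.

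**1. One window per sampling day.** Draws = 1 predose + 300/30 = 11. Volume = 11 × 4.5 mL × 2 days = 99 mL per period, and × 3 = 297 mL in total. Both match the figures in Protocol 6.5. Two windows a day would give 198 and 594 mL.

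**2. Dose sampled.** Each dose is 2 × 230 = 460 IU. The nominal gaps between dosing times are 6, 9 and 9 hours, all longer than 5.

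| Regimen, window | Active doses in window | Share of daily dose | Hours since previous active dose | Earlier active doses since Day 4 |
|---|---|---|---|---|
| qd evening | 1 | 460/460 = 100% | 24 | 4 |
| bid morning | 1 | 460/920 = 50% | 9 | 8 |
| bid evening | 1 | 50% | 15 | 9 |
| tid morning | 1 | 460/1380 = 33% | 9 | 12 |
| tid afternoon | 1 | 33% | 6 | 13 |
| tid evening | 1 | 33% | 9 | 14 |

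One dose per window is nominal. At the limits of the tolerances the tid 7am and 1pm doses can be 4 hours apart, so a morning window could overlap the next active dose by up to about 1 hour. The SAP's own 60-minute lag makes that minor.

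**3. Carry-over.** The documents give no half-life, so I assume a range. With mono-exponential decay and half-life h, a dose given g hours before the window adds 2^(−g/h) of the sampled dose's own 5-hour area. Carry-over is the sum over earlier doses. For tid afternoon at h = 4, the leading terms are 2^(−6/4) + 2^(−15/4) + 2^(−24/4) = 0.354 + 0.074 + 0.016, and all terms sum to 45.1%.

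| Assumed h | qd | bid | tid |
|---|---|---|---|
| 1 h | 0% | 0–0.2% | 0.2–1.6% |
| 2 h | 0% | 0.6–4.4% | 4.6–13.1% |
| 4 h | 1.6% | 9.1–22.9% | 27.4–45.1% |
| 6 h | 6.7% | 25.5–44.4% | 57.7–78.9% |

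The Day 8 minus Day 3 difference is not corrected for the Day 8 predose level, so any such carry-over stays in the areas.

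**4. Time of day.** The rules of Protocol 5.2 allow 1 slot pattern for placebo+qd+bid, 2 for placebo+qd+tid and 4 for placebo+bid+tid. Assuming 10 subjects per pair and equal use of the patterns, the expected windows are:

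| | Morning | Afternoon | Evening |
|---|---|---|---|
| qd | 0 | 0 | 20 |
| bid | 15 | 0 | 5 |
| tid | 7.5 | 10 | 2.5 |
| All active | 22.5 | 10 | 27.5 |
| Placebo | 7.5 | 20 | 2.5 |

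**5. Precision, in residual-SD units, under the same assumptions.**
- One-way layout: pooled √(1/60 + 1/30) = 0.224; per regimen √(1/20 + 1/30) = 0.289. This pool sets placebo that is two-thirds afternoon (20 of 30) against active that is mostly morning or evening (50 of 60), so it should not be used unadjusted.
- Subject and slot terms, SE from the diagonal of (X′X)⁻¹ over 90 periods: pooled 0.262; qd 0.514, bid 0.367, tid 0.302. The pooled SE is smaller by 1 − 0.262/0.514 = 49%, 1 − 0.262/0.367 = 29% and 1 − 0.262/0.302 = 13%.
- By slot without subject terms: morning √(1/22.5 + 1/7.5) = 0.42; afternoon √(1/10 + 1/20) = 0.39; evening √(1/27.5 + 1/2.5) = 0.66. With subject terms: 0.57, 0.53 and 0.83.

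The residual SD differs between models with and without subject terms, so SEs should be compared only within a model.

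**The case against.** The objective is worded against placebo. Three of the six pairs are regimen versus placebo, and those still describe the response after a dose. SAP 2.8.1 puts the question of multiple daily doses to the CGM data, and nothing in SAP 2.8.2 says that the PK/PD pairs speak to total daily exposure, so the misreading is a risk and not a plan. The study is Phase 2a and declared not powered. The slot allocation is in a separate randomization plan and the table shells are in a separate file, neither of which I have seen. All of this stands, and it limits the point to the active-versus-active pairs and the missing slot analysis. Lack of power is no answer to it, though: more subjects would not make a one-dose window measure several doses.

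A reader might go further and infer that the regimen contrasts must have expected value zero, that they cannot register multiple dosing at all, or that they test carry-over alone. The documents do not support this. The slots differ by regimen, so any time-of-day difference in drug effect makes the contrasts non-zero. Matching to Day 3 removes the baseline clock-time profile but not such a difference. Sampling also falls on the fifth treatment day, after 4 to 14 earlier active doses, and carry-over of unknown size can enter the areas.

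Pooling has limits too. It helps only with slot adjustment, and the evening estimate rests on very few placebo windows.

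**Conclusion.** The point holds for the active-versus-active comparisons. They contrast the response after one equal 460 IU dose, mixed with carry-over and time of day, and are not direct evidence on single versus multiple daily dosing. The dose shares of 100%, 50% and 33% follow from the documents at nominal times. Carry-over could be anywhere from negligible to most of the sampled dose's own area (0 to 79%) over assumed half-lives of 1 to 6 hours. The standard errors rest on 10 subjects per regimen pair and equal use of the allowed slots; if the randomization plan differs, they change. Under those assumptions, placebo is sampled in the evening about 2 to 3 times in 30. The point concerns secondary endpoints and leaves the primary CGM analysis untouched.

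**What to change.** In SAP 2.8.2:

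- Add as the main PK/PD contrast one active 460 IU dose versus placebo, pooled over regimens, in a model with subject and sampling-slot terms. Check the pooling assumption with a regimen term. The check is weak at this size, so report the estimate and its confidence interval rather than a pass/fail test.
- Report active versus placebo by sampling slot with confidence intervals, as Protocol 5.2 intends. State that the evening estimate is imprecise because few placebo windows fall there.
- Keep the regimen-versus-placebo results as per-dose contrasts.
- Make the active-versus-active comparisons descriptive. State that they reflect carry-over and time of day together and are not evidence on total daily exposure.
- Replace the assumed slot counts with those in the randomization plan.

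The cost is SAP wording and one extra model, with no new samples. The downside is that pooling assumes a similar per-dose response across regimens. Sampling after all three dosing times would need 3 × 99 = 297 mL per period and 891 mL per subject; this fix does not depend on it.
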